Serum carcinoembryonic antigen (CEA) o		X			X		X	X o				
Serum CA19-9 o		X			X		X	X o				
Laboratory Procedures/Assessments: Analysis performed by CENTRAL laboratory												
Blood for Genetics p			X									
Correlative Blood Samples (DNA) q			X	X	X				X			
Correlative Blood Samples (RNA) q			X	X	X				X			
Correlative Blood Samples (plasma) q			X									
Correlative Blood Samples (serum) q			X									
Efficacy Measurements												
Tumour Imaging r		X			X		X	X	X s		X s	
Tumour Tissue Collection												
Archival and/or Newly Obtained Tissue Collection t	X								X			

- a. Unless otherwise specified, assessments/procedures are to be performed on Day 1 and prior to the first dose of treatment for each cycle unless otherwise specified.
- b. In subjects who discontinue study therapy without documented disease progression, every effort should be made to continue monitoring their disease status by radiologic imaging every 6 weeks ( $\pm$  7 days) until (1) the start of new anti-cancer treatment, (2) disease progression as assessed by the central imaging vendor, (3) death, or (4) the end of the study, whichever occurs first.
- c. After documented local site assessed disease progression or the start of new anticancer treatment; contacts are approximately every 12 weeks by telephone. Updated survival status may be requested by the Sponsor at any time during the course of the study. Upon Sponsor notification all subjects who do not /will not have a scheduled study visit or study contact during the Sponsor defined time period will be contacted for their survival status (excluding subjects that have a death event previously recorded).
- d. Unless otherwise specified, the window for each visit is  $\pm$  3 days. Cycle 1 treatment should be given within 3 days of randomization.
- e. Written consent must be obtained prior to performing any protocol specified procedure. Results of a test performed prior to the subject signing consent as part of routine clinical management are acceptable in lieu of a screening test if performed within the specified time frame (eg, within 21 days prior to the first dose of trial treatment). Screening number will be assigned when the study informed consent is signed.

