- f. Signing the informed consent for future biomedical research (FBR) sample is optional. Detailed instructions for the collection and management of specimens for FBR are provided in the Procedures Manual and Section 12.2 of this protocol.
- g. Prior medications – Record all medications taken within 30 days of first dose. Concomitant medications – Enter new medications started during the trial through the Safety Follow-up visit. Record all medications taken for SAEs as defined in Section 7.2.
- h. Record all AEs occurring within 30 days after the last dose of trial treatment. Report all SAEs (related and unrelated to trial treatment) and ECIs occurring up until 90 days after the last dose of trial treatment or 30 days after the end of treatment if the subject initiates new anticancer therapy, whichever occurs first. Afterwards, report only SAEs and ECIs that are related to trial treatment.
- i. It is strongly recommended that electronic Patient Reported Outcomes (ePROs) are administered prior to drug administration, adverse event evaluation and disease status notification starting with the EQ5D-3L, followed by EORTC QLQ-C30, and EORTC QLQ-ST022; an exception to this recommendation may occur at the treatment discontinuation visit where subjects may have already been notified of their disease status or an AE evaluation is known prior to them arriving to the clinic. All ePROs are to be performed at Cycle 1, Cycle 2, Cycle 3, Cycle 4, Cycle 5 and every 2 cycles thereafter (eg, Cycle 7, Cycle 9) up to a year or End of Treatment, whichever comes first, and the 30-day post-treatment discontinuation follow-up visit. If the subject does not complete the ePROs the MISS\_MODE form must be completed to capture the reason the assessment was not performed.
- j. Vital signs to include temperature, pulse, respiratory rate, weight and blood pressure. Height will be measured at Visit 1 only.
- k. Pembrolizumab should be administered on Day 1 of each 3-week cycle after all procedures/assessments have been completed. Pembrolizumab 200 mg fixed dose should be administered as a 30-minute IV infusion Q3W. Sites should make every effort to target infusion timing to be as close to 30 minutes as possible. However, given the variability of infusion pumps from site to site, a window of -5 minutes and +10 minutes is permitted (ie, infusion time is 30 minutes: -5 min/+10 min). Study treatment is discontinued after completion of 35 administrations (approximately 2 years).

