Urinalysis p		X										
T3 (or Free T3), FT4 and TSH p		X		X		X		X		X		
Serum carcinoembryonic antigen (CEA) q		X			X		X	X q				
Serum CA19-9 q		X			X		X	X q				
Laboratory Procedures/Assessments: Analysis performed by CENTRAL laboratory												
Blood for Genetics f			X									
Correlative Blood Samples (DNA) s			X	X	X				X			
Correlative Blood Samples (RNA) s			X	X	X				X			
Correlative Blood Samples (plasma) s			X									
Correlative Blood Samples (serum) s			X									
Efficacy Measurements												
Tumour Imaging t		X			X		X	X t	X u		X u	
Tumour Tissue Collection												
Archival or Newly Obtained Tissue Collection v	X								X			

- a. Unless otherwise specified, assessments/procedures are to be performed on Day 1 and prior to the first dose of treatment for each cycle unless otherwise specified.
- b. In subjects who discontinue study therapy without documented disease progression, every effort should be made to continue monitoring their disease status by radiologic imaging every 6 weeks ( $\pm$  7 days) until (1) the start of new anti-cancer treatment, (2) disease progression as assessed by the central imaging vendor, (3) death, or (4) the end of the study, whichever occurs first.
- c. After the start of new anti-cancer treatment or documented disease progression by the central imaging vendor, the subject should be contacted by telephone every 12 weeks to assess for survival status. Note: Every effort should be made to ensure telephone contact at least 90 days post discontinuation to capture SAEs/ECIs. The Sponsor may request survival status be assessed at additional time points during the course of the study. For example, these additional time points may be requested prior to; an eDMC safety review, efficacy interim analysis, and/or final analysis. All subjects who are not known to have died prior to the request for these additional survival status time points will be contacted at that time.
- d. Unless otherwise specified, the window for each visit is  $\pm$  3 days. Cycle 1 treatment must be given within 3 days of randomization.

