**6.2 Second Course Phase (Retreatment with Pembrolizumab)**

Trial Period:	Treatment Cycles a						End of Treatment	Post-Treatment		
Treatment Cycle:	1	2	3	4	5	Cycle 6 and beyond	Last Dose	Safety Follow-up	Follow Up Visits b	Survival Follow-up c
							At time of treatment discon	30 days post discontinuation	Every 6 weeks post discontinuation	Every 12 weeks
Scheduling Window (Days) d :	-3	± 3	± 3	± 3	± 3	± 3	± 3	± 7	± 7	± 7
Administrative Procedures										
Eligibility Criteria e	X									
Concomitant Medication Review f	X	X	X	X	X	X	X	X		
Clinical Procedures/Assessments										
Review Adverse Events g	X	X	X	X	X	X	X	X	X	
Full Physical Examination	X						X			
Directed Physical Examination		X	X	X	X	X				
Vital Signs and Weight h	X	X	X	X	X	X	X	X		
ECOG Performance Status k	X	X	X	X	X	X	X			
Pembrolizumab Administration	X	X	X	X	X	X				
Post-study Anticancer Therapy Status									X	X
Survival Status n	←								→	X
Laboratory Procedures/Assessments: Analysis performed by LOCAL laboratory										
Pregnancy Test – Urine or Serum i	X	X	X	X	X	X		X		
PT/INR and aPTT j	X									
CBC with Differential k	X	X	X	X	X	X k	X	X		
Chemistry Panel k	X	X	X	X	X	X k	X	X		
Urinalysis k	X									
T3(or Free T3), FT4 and TSH k	X		X		X			X		
Efficacy Measurements										
Tumour Imaging l	X		X		X	X	X m		X m	

- a. In general, assessments/procedures are to be performed on Day 1 and prior to the first dose of treatment for each cycle unless otherwise specified. Treatment cycles are 3 weeks.
- b. In subjects who discontinue study therapy without documented disease progression, every effort should be made to continue monitoring their disease status by radiologic imaging every 6 weeks (42 ± 7 days) up to week 30 or every 9 weeks (± 7 days) if after Week 30, until (1) the start of new anti-cancer treatment, (2) disease progression as assessed by the central imaging vendor, (3) death, or (4) the end of the study, whichever occurs first.
- c. After the start of new anti-cancer treatment or documented disease progression by the central imaging vendor, the subject should be contacted by telephone every 12 weeks.

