### **7.2.3 Immediate Reporting of Adverse Events to the Sponsor**

#### **7.2.3.1 Serious Adverse Events**

A serious adverse event is any adverse event occurring at any dose or during any use of Sponsor's product that:

- Results in death;
- Is life threatening;
- Results in persistent or significant disability/incapacity;
- Results in or prolongs an existing inpatient hospitalization;
- Is a congenital anomaly/birth defect;
- Is an other important medical event

**Note:** In addition to the above criteria, adverse events meeting either of the below criteria, although not serious per ICH definition, are reportable to the Sponsor in the same timeframe as SAEs to meet certain local requirements. Therefore, these events are considered serious by the Sponsor for collection purposes.

- Is a cancer;
- Is associated with an overdose.

Refer to [Table 11](#) for additional details regarding each of the above criteria.

For the time period beginning when the consent form is signed until randomization/treatment allocation, any serious adverse event, or follow up to a serious adverse event, including death due to any cause other than progression of the cancer under study (reference Section 7.2.3.3 for additional details), that occurs to any subject must be reported within 24 hours to the Sponsor if it causes the subject to be excluded from the trial, or is the result of a protocol-specified intervention, including but not limited to washout or discontinuation of usual therapy, diet, placebo treatment or a procedure.

For the time period beginning at randomization/treatment allocation through 90 days following cessation of treatment, or 30 days following cessation of treatment if the subject initiates new anticancer therapy, whichever is earlier, any serious adverse event, or follow up to a serious adverse event, including death due to any cause other than progression of the cancer under study (reference Section 7.2.3.3 for additional details), whether or not related to the Sponsor's product, must be reported within 24 hours to the Sponsor either by electronic media or paper. Electronic reporting procedures can be found in the EDC data entry guidelines. Paper reporting procedures can be found in the Investigator Trial File Binder (or equivalent).

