**Table 14 Analysis Strategy for Safety Parameters**

Safety Tier	Safety Endpoint	p-Value	95% CI for Treatment Comparison	Descriptive Statistics
Tier 2	Any AE		X	X
	Any Grade 3-5 AE		X	X
	Any Serious AE		X	X
	Any Drug-Related AE		X	X
	Any Serious and Drug-Related AE		X	X
	Any Grade3-5 and Drug-Related AE		X	X
	Dose Modification due to AE		X	X
	Discontinuation due to AE		X	X
	Death		X	X
	Specific AEs, SOCs (including $\geq 4$ of subjects in one of the treatment groups)		X	X
Tier 3	Specific AEs, SOCs (incidence $< 4$ of subjects in all of the treatment groups)			X
	Change from Baseline Results (Labs, ECGs, Vital Signs)			X

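### The SAE/ECI reporting window is 90 days in every arm, but only the Arms 2 and 3 flow chart tells sites to try to telephone subjects at 90 days or later to capture these events

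*Combined protocol and SAP*

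**What the plan says.** **Reporting duty.** Section 7.2.3.1 sets one SAE window for all arms, with the shorter limit applying once new anticancer therapy begins: "For the time period beginning at randomization/treatment allocation through 90 days following cessation of treatment, or 30 days following cessation of treatment". Section 7.2.3.2 sets the same window for ECIs, and Sections 2.1 and 5.8.1 repeat it. Footnote h, with the same shorter limit for new therapy, has the same text in the Arm 1 chart and in the Arms 2 and 3 chart: "ECIs occurring up until 90 days after the last dose of trial treatment or 30 days after the end of treatment".

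**Contact to find the events.** In the Arms 2 and 3 chart, footnote c includes the note "Every effort should be made to ensure telephone contact at least 90 days post discontinuation to capture SAEs/ECIs". In the Arm 1 chart, footnote c reads "After documented local site assessed disease progression or the start of new anticancer treatment; contacts are approximately every 12 weeks by telephone" and goes on to survival-status requests. It does not mention SAEs or ECIs. The second-course chart (Section 6.2, footnote c) also lacks the note. Its contact is for survival status, at 12-week intervals: "After the start of new anti-cancer treatment or documented disease progression by the central imaging vendor, the subject should be contacted by telephone". Sections 7.1.5.3.1 to 7.1.5.4, which cover post-treatment visits and survival status for all arms, do not contain it either.

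**Use of the data.** Table 14 lists "Any Serious AE" as a Tier 2 endpoint, reported with 95% confidence intervals for differences between treatments.

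**The concern.** A site can report only the events it learns of. Section 7.1.2.1 makes the flow chart the schedule for AE assessment, so a contact present in one chart and absent from another means that the arms are searched with different intensity over the same window. Arm 1 is open label and its serious-AE percentage is set beside those of Arms 2 and 3. If late events are sought in two arms and mainly volunteered in the third, equal true rates would tend to look lower on monotherapy.

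Late events are not a side issue for this drug. Section 5.2.1.2.1 states that immune-related events may appear several months after the last pembrolizumab dose. No passage gives a reason for following monotherapy subjects less actively.

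**Working it through.** The plan gives no figure to reproduce. The check sets the three charts side by side and does the calendar arithmetic.

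| Item | Arm 1 (6.1.1) | Arms 2 and 3 (6.1.2) | Second course (6.2) |
|---|---|---|---|
| SAE/ECI window | 90 days, or 30 with new therapy | same | same |
| Safety Follow-up visit | 30 days | 30 days | 30 days |
| AE review at 6-weekly Follow-up Visits | marked | marked | marked |
| AE review under Survival Follow-up | not marked | not marked | not marked |
| Survival telephone contact | about every 12 weeks | every 12 weeks | every 12 weeks |
| Note on a contact at 90 days or later for SAEs/ECIs | absent | present | absent |

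**Who falls in the gap.**
- A subject who stops without progression goes to the 6-weekly Follow-up Visits, where AE review is marked in every chart.
- For a subject who starts new anticancer therapy, the window closes at 30 days, about when the safety visit takes place.
- A subject who stops for progression, is alive and starts no new therapy goes to Survival Follow-up with the 90-day window still open. Only this group is affected.

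**Length of the gap.** The last AE review marked for this group is the 30-day visit: 90 − 30 = 60 days. With the ±7-day window, that visit falls on days 23 to 37, so 90 − 37 = 53 to 90 − 23 = 67 days remain.

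**Whether the survival call fills it.** 12 weeks = 84 days, with a window of ±7 days. The documents do not say when the clock starts.
- Counted from discontinuation, the first call falls on days 77 to 91. Most of that range lies before day 90.
- Counted from a visit on day 30, it is due on day 30 + 84 = 114, and no earlier than 114 − 7 = 107, after the window has closed.

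On either count, Section 7.1.5.3.3 gives the purpose of the call as survival status. Nothing asks the site to enquire about SAEs or ECIs, so the survival call does not replace the note. A call made at least 90 days after discontinuation for that purpose, as in Arms 2 and 3, can look back over the whole window.

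**The case against.** Several points on the other side stand.

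- The note asks for every effort and sits in a survival-call footnote. It is not a scheduled procedure, and even in Arms 2 and 3 it has no mark in the AE review row.
- The duty to report within 24 hours is the same in all arms. Under Section 7.2.3.1, an SAE considered related must be reported whenever the investigator learns of it, so a late immune-related event judged related and known to the site is reportable in Arm 1 without the note.
- The affected group is only part of the arm, and progression of the cancer under study is itself excluded from SAE reporting (Section 7.2.3.3).
- Section 8.6.2 names no Tier 1 events and treats the Tier 2 intervals as descriptive. Arms 2 and 3 share one chart, so the blinded comparison is untouched.
- The difference looks like a drafting omission. Arm 1 footnote c is nearly the same text as footnote x of the Arms 2 and 3 chart. Arms 2 and 3 have both texts and Arm 1 only one. This is inference.

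These points limit the reach and weight of the problem. They do not remove it: a duty to report does not bring an unknown event to the site's attention, and no other passage gives Arm 1 the contact.

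A reader might infer more than the documents support:

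- That Arms 2 and 3 have a mandatory day-90 contact. The wording is best effort.
- That the bias can be stated in percentage points. The documents give no late-SAE rate, no capture rate with or without the call, and no count of subjects in the gap. A figure would rest on assumed rates, and applying it to the whole arm would overstate it.
- That the error must always favour monotherapy. That is the expected direction if sites follow the charts as written, but it is not demonstrated.
- That the second-course omission adds to the bias between arms. That chart is common to all retreated subjects, and Section 7.1.2.6.4 makes the placebo arm ineligible, so the omission concerns completeness of safety capture.

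**Conclusion.** The concern holds as an internal inconsistency between flow charts. The reporting window is the same in every arm, but the instruction to look for events at its end is given for Arms 2 and 3 only. The consequence is a stretch of about 60 days without a scheduled safety contact for Arm 1 subjects who stop for progression and start no new therapy. Under-capture of late SAEs and ECIs in Arm 1 is the expected effect on the descriptive serious-AE comparison.

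The size cannot be computed from the documents and is probably modest. The conclusion assumes that sites follow the charts as written, that the note leads to some calls that would otherwise not be made, and that the serious-AE row of Table 14 counts events to the end of the 90-day window, which Section 8.6.2 does not state. The efficacy hypotheses are not affected.

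**What to change.** Add the sentence on the 90-day SAE/ECI contact from footnote c of Section 6.1.2 to footnote c of Section 6.1.1. Show the contact in the adverse-event review row of both charts under Survival Follow-up, for subjects whose reporting window is still open. Add the same sentence to footnote c of Section 6.2, for completeness of safety capture and not as a correction between arms.

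The cost is one sentence in each of two footnotes, a mark in the charts, and at most one telephone call per affected subject, often combined with a survival call. Timing matters, because an event missed in this period may not be recoverable later.
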